#### 6.4.6.2 *Treated Migraine Days per Month*

The number of treated migraine days per month is derived as follows:

- Month during LTT:
  - If the total number of study days in the month < 14: total number of treated migraine days in the month (i.e., no proration)
  - If the total number of study days in the month  $\geq 14$ :  $28 \times (\text{total number of treated migraine days in the month}) / (\text{total number of study days in the month})$
- Overall LTT:
  - If the total number of study days in the LTT analysis period < 14: total number of treated migraine days in the LTT analysis period (i.e., no proration)
  - If the total number of study days in the LTT analysis period  $\geq 14$ :  $28 \times (\text{total number of treated migraine days in the LTT analysis period}) / (\text{total number of study days in the LTT analysis period})$ .

All study days from LTT start to LTT end are included in analyses, not only days of data.

The following tables are produced for the safety analysis set:

- Number and percentage of subjects in the following categories based on the number of treated migraine days per month in the overall LTT by migraine intensity (total; moderate or severe): 0,  $> 0$  to  $< 1$ ,  $\geq 1$  to  $< 2$ ,  $\geq 2$  to  $< 3$ ,  $\geq 3$  to  $< 4$ ,  $\geq 4$  to  $< 5$ ,  $\geq 5$  to  $< 6$ ,  $\geq 6$  to  $< 7$ ,  $\geq 7$  to  $< 8$ ,  $\geq 8$ ,  $< 2$ ,  $\geq 2$ . The last 2 categories for total migraine intensity align with subgroups specified in Section 4.3.
- Number and percentage of subjects in the above categories based on the maximum number of treated migraine days per month in any 1 month during LTT by migraine intensity.

These tables are also produced for the safety analysis set with  $\geq 51$  weeks in the LTT analysis period (see Section 6.2.6.1).

#### 6.4.7 *Safety Narratives*

A by-subject listing of safety narrative subject identifiers is provided for the following select events, safety analysis periods, and analysis sets as columns:

- Deaths (across all safety analysis periods) for the enrolled analysis set
- SAEs during pre-treatment (only if subject received zavegepant in previous studies BHV3500-201/301), on-treatment, and follow-up for the enrolled analysis set
- AEs leading to discontinuation of study drug (across all safety analysis periods) for the safety analysis set

- On-treatment events of special interest for the safety analysis set:
  - AST or ALT > 3x ULN
  - AST or ALT > 3x ULN concurrent with TBL > 2x ULN
  - TBL > 2x ULN
  - ALP > 2x ULN
  - Select hepatic-related AEs, i.e., PTs containing cirrhosis, hepatic failure, hepatitis, jaundice, or liver failure
  - Local irritation AEs of severe intensity
  - Cardiovascular AEs
  - Suicidality AEs.

Refer to the Zavegeptan Core SAP for additional details.

## 6.5 Outcomes Research

Outcomes research questionnaires and rating scales are MSQ, MIDAS, CGI-c, PoM, and SM. Outcomes research endpoints are assessed for the safety analysis set.

Measurements are first slotted into the pre-LTT, LTT and follow-up analysis periods, and then slotted into analysis visits. If a subject has multiple values in an analysis visit window, then the non-missing value assessed closest to the target date for the visit is used; in the case of a tie, the last value assessed and entered is used. See Sections 6.2.4, 7.2, and 7.3 for definitions of baseline, analysis periods, and analysis visit windows, respectively.

Parameters are summarized at baseline, each scheduled visit, and end of study (EOS), as applicable. EOS is defined as the last non-missing post-baseline value assessed and entered in the study.

By-subject listings of outcomes research questionnaires and rating scales (i.e., MSQ; MIDAS; CGI-c; PoM, and SM) are provided for the enrolled analysis set. All listings except PoM and SM display COVID-19 visit impact code for visits impacted by COVID-19 (see Section 9.1.5.2).

Refer to the Zavegeptan Core SAP for detailed descriptions of these questionnaires and rating scales and listing contents.

### 6.5.1 MSQ

Impact of treatment on patient-reported quality of life is assessed using the MSQ, which is a 14-item questionnaire that has been validated in migraine patients to assess the effects of migraines on their daily activities over the past 4 weeks. The MSQ is evaluated at the following visits: Pre-Baseline; Weeks 12, 24, 36 and 52; and early termination.

The MSQ consists of the following 3 domains: (1) restrictive role function, (2) preventive role function and (3) emotional function. Values and changes from baseline in transformed scores for each domain are tabulated descriptively as continuous variables (including 2-sided 95% normal CIs for mean change) at baseline, each scheduled post-baseline visit, and EOS. Refer to the Zavegeptan Core SAP for deriving transformed scores for each domain.

#### **6.5.2 PoM**

The PoM is a 5-point rating scale that measures the patient's preference of study medication to previous medications to treat migraine pain. The PoM is evaluated with the eDiary at early termination and Week 52.

The number and percentage of subjects in each category are tabulated at Week 52 and EOS, including 2-sided exact Clopper-Pearson 95% CIs for each percentage. Refer to the Zavegeptan Core SAP for categories.

#### **6.5.3 SM**

The SM is a 7-point rating scale that captures the subjects' perception of whether they are satisfied with their headache medication. The SM is evaluated with the eDiary at early termination and Week 52.

The number and percentage of subjects in each category are tabulated at Week 52 and EOS, including 2-sided exact Clopper-Pearson 95% CIs for each percentage. Refer to the Zavegeptan Core SAP for categories.

#### **6.5.4 MIDAS**

The MIDAS is a retrospective, patient-administered, 5-item questionnaire that measures headache-related disability as lost time due to headache from paid work or school, household work and non-work activities. The MIDAS is evaluated at the following visits: Pre-Baseline; Weeks 12, 24, 36, and 52; and early termination.

Values and changes from baseline in the total, absenteeism, presenteeism, and item scores are tabulated descriptively as continuous variables (including 2-sided 95% normal CIs for mean change) at baseline, each scheduled post-baseline visit, and EOS. Refer to the Zavegeptan Core SAP for calculating the total, absenteeism, presenteeism, and item scores.

#### **6.5.5 CGI-c**

The CGI-c is an observer-rated 7-point scale that measures patient total improvement relative to the investigator's past experience with other patients with the same diagnosis, with or without collateral information. The CGI-c is evaluated at early termination and the following visits: Weeks 12, 24, 36 and 52.

The number and percentage of subjects in each category are tabulated at each scheduled post-baseline visit and EOS, including 2-sided exact Clopper-Pearson 95% CIs for each percentage. Refer to the Zavegeptan Core SAP for categories.

## 6.6 COVID-19 Impact

Analyses are based on COVID-19 visit impact data with non-missing COVID-19 visit dates (see Section 9.1.1).

Measurements are slotted into analysis periods according to COVID-19 visit dates.

When COVID-19 visit impact is summarized descriptively over time, measurements are first slotted into analysis periods. Next, measurements are slotted into analysis visits in these analysis periods (see Section 7.3).

### 6.6.1 COVID-19 Overall Impact

COVID-19 overall visit impact is tabulated for the safety analysis set. The number and percentage of subjects in the categories and subcategories defined by COVID-19 visit impact type, COVID-19 visit impact characteristics, and COVID-19 visit impact relationship are tabulated (see Section 9.1.1). In addition, for each of the 3 COVID-19 visit impact type categories (i.e., missed visit; in-person; remote visit), the number and percentage of subjects in the following subcategories defined by the number of visits impacted are tabulated:  $\geq 2$  visits, ...,  $\geq 12$  visits. Visit counts are based on unique COVID-19 visit dates. Percentages are based on subjects with  $\geq 1$  visit with non-missing COVID-19 visit impact (see Section 9.1.3).

### 6.6.2 COVID-19 Impact over Time

COVID-19 visit impact is tabulated at each analysis visit for the safety analysis set. The number and percentage of subjects in the categories and subcategories defined by COVID-19 visit impact type, visit impact characteristics, and visit impact relationship are presented for each analysis period (pre-LTT, LTT, follow-up) and analysis visit. Percentages are based on subjects with  $\geq 1$  visit with non-missing COVID-19 visit impact in the analysis visit window.

Missing LFT data impacted by COVID-19 are tabulated at each analysis visit for the safety analysis set as the number and percentage of subjects in the following categories:

- 1) Missing LFT data, defined as missing values for all of the 4 following LFTs in the analysis visit window: ALT, AST, ALP, and TBL.
- 2) Missing LFT data at visits impacted by COVID-19, i.e., meeting criteria (1) and having  $\geq 1$  visit impacted by COVID-19 in the analysis visit window (see Section 9.1.3)
- 3) Missing LFT data at missed visits due to COVID-19, i.e., meeting criteria (1), (2), and having  $\geq 1$  missed visit in the analysis visit window (see Section 9.1.1).

Percentages are based on evaluable subjects at each analysis visit in each analysis period (pre-LTT, LTT, follow-up). A subject is evaluable at an analysis visit during pre-LTT or LTT if the study day corresponding to the last contact date is  $\geq$  lower bound of the analysis visit window. A subject is evaluable at an analysis visit during follow-up if the follow-up day corresponding to the last contact date is  $\geq$  lower bound of the analysis visit window. See Section 7.1 for derived dates, and Section 7.3 for study days and follow-up days.

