## **7 CONVENTIONS**

### **7.1 Derived Dates**

Derived dates for defining analysis periods are defined as follows:

- Study drug date/time: Complete finding date/time corresponding to “yes” response to question about taking study medication and number of sprays  $> 0$  in the eDiary evening report or medication reconciliation form.
- Study drug start date/time: Earliest study drug date/time.
- Study drug end date/time: Latest study drug date/time.
- Study drug last date/time: Study drug end date/time derived only for subjects with non-missing response to the question “Did the subject complete the study?” on the Study Exit Status CRF. Thus, in an interim analysis, all post-baseline data are included for a subject who is still on study. At the last database lock, the study drug last date is equal to the study drug end date.
- LTT start date/time: Earlier of (1) study drug start date/time, and (2) IWRS baseline visit date (i.e., Baseline/Day 1 visit date from the BHV3500\_202 IWRS Visit Report csv file).
- LTT end date/time: Later of (1) latest complete finding date/time in the eDiary on or after the LTT start date/time, and (2) latest complete visit date on or after the LTT start date through the Week 52/Early Termination visit date, and excluding the Follow-up Week 2 visit date, from the Visit Date CRFs.

- LTT last date/time: LTT end date/time derived only for subjects with non-missing response to the question “Did the subject complete the study?” on the Study Exit Status CRF. Thus, in an interim analysis, all LTT data are included for a subject who is still on study. At the last database lock, the LTT last date is equal to the LTT end date.
- OP start date/time: Earliest complete finding date/time in the eDiary before the LTT start date/time.
- OP end date/time: Latest complete finding date/time in the eDiary before the LTT start date/time.
- COVID-19 visit date: (1) Complete visit date, if it exists; (2) otherwise, complete date the visit was planned to occur for a missed visit (see Section 9.1.1).

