- Last contact date: (1) Earliest complete death date from the AE CRF, if it exists; (2) otherwise, the maximum complete date of the following: AE start or stop; COVID-19 visit only for in-person or remote visits; ECG; eDiary finding; informed consent; IWRS baseline visit; laboratory test collection; nasal inspection; non-study medication start or stop; physical exam; physical measurement; procedure; rating scale; questionnaire; vital sign; visit. If the last contact date is after the most recent raw database creation date, then it is set to the most recent raw database creation date.
- Death date: Last contact date derived only for subjects who died (see Section 6.4.1).

No imputations are performed on these derived dates. Complete dates are those with valid, non-missing day, month, and year.

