## 7.2 Analysis Periods

Analysis periods are defined as follows:

- OP: measurement date/time on or after the OP start date/time through the OP end date/time. This period is used to assess the number of migraine days per month during the OP.
- Pre-treatment: measurement date/time on or before the study drug start date/time. This period is used to derive baseline values, and to assess safety and outcomes research endpoints. Note that all measurements are pre-treatment for subjects in the enrolled analysis set with missing study drug start date.
- Pre-LTT: measurement date/time on or before the LTT start date/time. This period is used to derive analysis visit windows for slotting observations. Note that all measurements are pre-LTT for subjects in the enrolled analysis set with missing LTT start date.
- LTT: measurement date/time after the LTT start date/time through the LTT last date. This period is used to derive analysis visit windows for slotting observations, and to assess exposure and migraine days during LTT. Note that AEs with imputed start date equal to the

LTT start date are part of this period (refer to the Zavegeptan Core SAP for AE start date imputation).

- Follow-up: measurement date after the LTT last date. This period is used to slot observations.
- On-treatment safety: measurement date/time after the study drug start date/time through the study drug last date + 7 days. This period is used to assess safety endpoints on treatment.  
Note that AEs with imputed start date equal to the study drug start date are part of this period.
- Follow-up safety: measurement date after the study drug last date + 7 days. This period is used to assess safety endpoints during follow-up.

See Section 7.1 for derived dates for determining analysis periods. If measurement time is missing, not collected, or not applicable for a parameter, then the measurement date is compared to the derived date.

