### 7.3 Analysis Visit Windows

Refer to Protocol Section 4.3 for the schedule of assessments.

Study days are calculated from the LTT start date as follows:

- Measurement date – LTT start date + 1, if measurement date  $\geq$  LTT start date
- Measurement date – LTT start date, if measurement date  $<$  LTT start date.

Treatment days are calculated from the study drug start date as follows:

- Measurement date – study drug start date + 1, if measurement date  $\geq$  study drug start date
- Measurement date – study drug date, if measurement date  $<$  study drug start date.

Follow-up days are calculated from the LTT last date as follows:

- Measurement date – LTT last date, if measurement date  $\geq$  LTT last date + 1
- Measurement date – LTT last date – 1, if measurement date  $<$  LTT last date + 1

Evaluation intervals are based on study days in the LTT analysis period and follow-up days in the follow-up analysis period (see Section 7.2). Table 3 presents analysis visit windows.

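### In the missing-LFT table, evaluability at an LTT visit runs to last contact, so some early discontinuers count as missing in a window that opens after their LTT period ended

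*SAP*

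**What the plan says.** SAP 6.6.2 plans a table of missing liver function tests by analysis visit, with three nested categories. Category (1) is "missing values for all of the 4 following LFTs in the analysis visit window". Category (2) adds a COVID-19-impacted visit in the same window, and category (3) adds a missed visit. Percentages are taken over evaluable subjects. Under the LTT rule, a subject is evaluable if the "study day corresponding to the last contact date is" at or above the window's lower bound. Nothing in the section stops the rule at the end of LTT.

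The dates it relies on are defined elsewhere in the SAP:

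- **Last contact (7.1).** Except for subjects who died, it is "the maximum complete date of the following: AE start or stop", and the list goes on to "laboratory test collection; nasal inspection; non-study medication start or stop; physical exam; physical measurement; procedure; rating scale; questionnaire; vital sign; visit". The follow-up visit is not carved out.
- **LTT end (7.1).** It is the later of the last eDiary record and the last visit through Week 52 or early termination, "and excluding the Follow-up Week 2 visit date, from the Visit Date CRFs".
- **Period (7.2).** "Follow-up: measurement date after the LTT last date".
- **Windows (7.3).** "Evaluation intervals are based on study days in the LTT analysis period and follow-up days in the follow-up analysis period".

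Protocol 4.1 expects early discontinuers as well as completers to attend a follow-up visit about 14 days after EOT; the synopsis gives ± 2 days. SAP 6.4.2 schedules LFTs at both early termination and Follow-up Week 2.

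**The concern.** The denominator and the data follow different clocks. A subject stays in the LTT denominator until last contact, but LTT data stop at LTT end. Any LTT window whose lower bound falls between the two dates can hold no LFT from that subject, and the table still reports one as missing.

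Take a subject with an EOT visit and LFT on Day 145 (Week 20 window, Days 127 to 154) and a follow-up visit and LFT on Day 159. Every LFT scheduled at those two visits was drawn. Contact on Day 159 makes the subject evaluable at Week 24 (Days 155 to 182), where no LTT-period LFT can exist, so the subject falls in category (1). The same blood draw counts as present at Follow-up Week 2.

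What is at stake is whether this table describes LFT completeness correctly. The error has one direction: category (1) is too high. Categories (2) and (3) gain no subjects, because a COVID-19-affected follow-up visit is itself slotted to the follow-up period, but their percentages are taken over a denominator that is too large.

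**Working it through.** The plan states no figure for evaluability, discontinuation or missing LFTs, so there is none to reproduce.

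**Inputs from the documents**

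- LTT window lower bounds (SAP Table 3): Days 1, 22, 43, 71, 99, 127, 155, 183, 211, 239, 267, 295, 323, 351.
- Follow-up visit f = 12 to 16 days after EOT (protocol synopsis).
- 600 treated subjects (SAP 5).

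**Assumptions, not in the documents**

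- EOT days spread evenly over Days 1 to 350.
- LTT ends at the EOT visit, with no later diary record.
- Last contact is the follow-up visit.
- Discontinuation of 20% to 40%, and the attendance rates shown below.

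**Share of discontinuers affected.** A subject with EOT on Day D is wrongly evaluable in a window with lower bound L when D < L ≤ D + f. Each of the 13 lower bounds after Day 1 catches f days of D, and no day is caught twice, because the windows are at least 21 days wide.

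- f = 14: 13 × 14 / 350 = 182/350 = 52%
- f = 12: 13 × 12 / 350 = 156/350 = 45%
- f = 16: 13 × 16 / 350 = 208/350 = 59%

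Within the 28-day windows alone the figure at f = 14 is 14/28 = 50%; within the 21-day Week 2 and Week 4 windows it is 14/21 = 67%.

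**EOT at a scheduled visit.** The nominal visit day is 7 × week + 1 (the protocol gives Week 4 as Day 29). From Week 4 to Week 48, nominal day + 14 equals the next lower bound exactly, for example 85 + 14 = 99. With EOT at ± 7 days and follow-up at ± 2 days, 40 of the 75 combinations reach the bound (53%) for Weeks 8 to 48. At Week 4 (± 2 and ± 2) it is 15 of 25 (60%). At Week 2 all do.

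**Attendance.** 0.52 × 0.80 = 42%; 0.52 × 0.60 = 31%.

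**Size per visit.** With discontinuation rate d, 600d/350 subjects stop per day, so each lower bound from Day 22 on picks up 14 × 600d/350 = 24d extra subjects. Correctly evaluable subjects number 600 − (600d/350)(L − 1). The extra share of the denominator is extra / (correct + extra):

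| d (assumed) | Extra per visit | Week 4 (L = 22) | Week 24 (L = 155) | Week 52 (L = 351) |
|---|---|---|---|---|
| 20% | 4.8 | 4.8/597.6 = 0.8% | 4.8/552.0 = 0.9% | 4.8/484.8 = 1.0% |
| 30% | 7.2 | 7.2/596.4 = 1.2% | 7.2/528.0 = 1.4% | 7.2/427.2 = 1.7% |
| 40% | 9.6 | 9.6/595.2 = 1.6% | 9.6/504.0 = 1.9% | 9.6/369.6 = 2.6% |

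These rows assume full follow-up attendance. If the true missing rate is m, category (1) rises by (1 − m) times the tabulated share.

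**Dilution of categories (2) and (3).** At d = 30%, a hypothetical category (2) figure of 5.0% at Week 24 becomes 5.0% × 520.8/528.0 = 4.9%.

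**After the change.** The condition becomes D < L ≤ D, which no day satisfies, so the spurious count is zero.

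**The case against.** The strongest reply is that very little depends on this table. That is right. A reader might infer that the liver-safety findings are compromised, or that the trial could no longer show whether liver monitoring was adequate. The documents do not support that: the LFT estimands in SAP Table 2 use subjects with LFT data, SAP 6.4.2.2 tabulates elevations by analysis period, and neither uses the evaluability rule. No section gives the COVID-19 table the task of certifying liver monitoring.

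Three further limits stand.

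- **Not every LTT visit is inflated.** The Week 2 window opens on Day 1, so every treated subject is evaluable there under either rule.
- **Half of all early discontinuers is not a fixed share.** It presumes that they attend follow-up. Protocol 6.6 exempts from EOT procedures those who withdraw consent for all procedures, and 6.6.1 provides for loss to follow-up; both lower the share. AE or medication stop dates after the follow-up visit would raise it.
- **Completers reaching the Extension window (Day 379 on) are not shown to be a problem.** The footnote to Table 3 says that visit is displayed primarily in listings, and nothing establishes that it appears in this table.

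The objection leaves the mechanism untouched: neither 6.6.2 nor the definitions it relies on caps evaluability at the end of LTT.

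**Conclusion.** The point holds as a limited error in one descriptive table. The mechanism follows from the SAP's own definitions and needs no assumption; its size does. With full attendance at 14 ± 2 days and evenly spread EOT days, about 52% of early discontinuers (45% to 59%) are counted once as missing in a window that cannot hold their LFT, falling to about 42% or 31% at 80% or 60% attendance. At 20% to 40% discontinuation of 600, that is about 5 to 10 subjects and roughly 1 to 3 percentage points in category (1) at each visit from Week 4 on. The dilution of categories (2) and (3) is slight. No primary or hepatic endpoint changes.

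**What to change.** In SAP 6.6.2, split the joint pre-LTT/LTT rule. For an LTT analysis visit, define a subject as evaluable if the study day of the LTT end date (SAP 7.1) is at or above the lower bound of the window. Keep the last contact date for pre-LTT visits and, as follow-up day, for follow-up visits. LTT end date suits both reports, because SAP 7.1 derives it for ongoing subjects as well, whereas LTT last date exists only once study exit status is recorded.

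The cost is one phrase in the SAP and one variable in the table program, with no change to data collection. One smaller imprecision remains: windows open before the visit is due. Week 12, for example, opens on Day 71, while the visit at nominal Day 85 ± 7 is not due before Day 78. A subject whose LTT record ends in between, without an EOT visit, would still count as missing; a table footnote would cover this.
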